**14.0 Body Fluid Biospecimens: None**

## 15.0 Drug Information

F-DOPA is an investigational PET tracer utilized for the study under a Mayo physician-sponsor IND #61300 held by [name] in the division of Nuclear Medicine. The F-DOPA is produced in the Mayo Clinic PET Radiochemistry Facility using Good Manufacturing Practice as defined by 21 CFR Part 212.

The literature reports no deleterious effect was revealed in toxicity testing of F-DOPA-PET, and concludes the toxicological safety of the product is guaranteed given the toxicity data of the various potential impurities. F-DOPA-PET is currently in production at this institution, and is used to image malignant gliomas for research studies MC 1373 (IRB 13-005102) and MC 1374 (IRB 13-005106).

## 16.0 Statistical Considerations and Methodology

### 16.1 Study Overview

This is a single-arm, single-stage phase II Simon's Optimum study with an analysis that will compare progression-free survival (PFS) at 3 months for recurrent glioma patients after radiotherapy targeting volumes designed with both F-DOPA-PET and MRI information with historical controls.

16.11 The primary endpoint of this trial is the proportion of patients that experience progression-free survival at 3 months based on our hypothesis that the combination of more accurate target delineation of high-grade glioma by F-DOPA-PET will improve overall tumor control.

### 16.2 Statistical Design

#### 16.21 Decision Rules

The primary endpoint of this trial is the proportion of patients treated with F-DOPA-PET guided radiotherapy who are alive and have not progressed within 3 months. A success will be a patient who is alive and without evidence of progressive disease within 3 months from registration. Median PFS after bevacizumab failure ranges between 1-2 months.[17, 34] Thus, the largest success proportion where the proposed treatment would be considered ineffective in this population is 20%. The following Simon's Optimum design uses 20 patients to test the null hypothesis that the proportion of successes is at most 20% with an overall significance level (alpha) of 0.186, and a power of 85.9% to detect a true success proportion of 40%.

16.22 After 10 evaluable patients are accrued to this study and followed for at least 3 months, if 2 or more successes are alive and progression-free at 3 months, the results will wait until conclusion of the study. If 1 or fewer patients are alive without evidence of progression at 3 months, the study will be stopped and the treatment will be deemed ineffective in this population.

16.23 After 20 evaluable patients are accrued to this study and followed for at least 3 months, if 6 or more successes are observed we may recommend further testing of this regimen in subsequent studies in this patient population.

16.24 We will not suspend accrual between stages to allow the first 20 patients to become evaluable, unless undue toxicity is observed.

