## 2.0 Goals

### 2.1 Primary

- 2.11 Compare the progression-free survival rate at 3 months for recurrent high-grade glioma patients after reirradiation targeting volumes designed with both  $^{18}\text{F}$ -DOPA-PET and conventional MRI with historical controls

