#### 4.0 Test Schedule

Tests and procedures	Baseline (<21 days prior to registration)	Radiation Treatment Planning	During Radiation Treatment	End of Radiation Treatment +/- 3 days	1 month post RT +/- 7 days	3 months post RT +/- 14 days	At every clinically indicated follow-up 
Physical examination, weight, ECOG PS	X			X	X	X	X
Neurologic history and examination	X 			X	X	X	X
Document current medications	X			X	X	X	X
Pregnancy test	X 						
QOL Assessment: MDASI-BT and BFI 	X 			X	X	X	X 
Standard Mayo glioma brain MRI with and without contrast		X 			X	X	X 
 F-DOPA-PET		X 3,R					
 F-DOPA adverse event assessment		X 					
CT simulation for radiotherapy planning		X 					
Adverse event assessment 	X		X 	X	X	X	X

1. For women of childbearing potential only. Must be done  $\leq 48$  hours prior to injection of study drug. Note: For a positive pregnancy test prior to the pre-RT  $^{18}\text{F}$ -DOPA injection the patient will not undergo the  $^{18}\text{F}$ -DOPA PET scan and will instead be taken off study with no follow-up.
2.  $^{18}\text{F}$ -DOPA post-injection AE assessment: done approximately 40-45 minutes post injection of  $^{18}\text{F}$ -DOPA by the Nuclear Medicine technologist performing the study. If an AE was observed, a second AE assessment is required  $\leq 24$  hours post injection. This assessment will be completed by the study staff. This information will be used for MCCC DSMB review (Section 16.91) and reporting of any AEs under  $^{18}\text{F}$ -DOPA IND (Section 10.0).
3. Must be completed  $\leq 14$  days prior to the start of radiotherapy.
4. CT simulation can be performed prior to or after registration.
5. All follow-up serial imaging after initial treatment will occur until progression or up to 2 years. Typical timing of scans is every 2-3 months or until progression. However, the actual timing of scans for protocol patients will be per the clinician's discretion.
6. To be assessed by Radiation Oncologist at baseline and during radiotherapy and Medical Oncologist for follow-up assessments for MCCC DSMB review (Section 16.91). Adverse events will be assessed weekly during routinely scheduled management visits (+/- 3 days)
7. Maximum grade of adverse events experienced during radiotherapy can be recorded at the end of treatment.

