## 11.416 Summary of the RANO Response Criteria Table

	CR	PR	SD	PD 	Preliminary PD/PsP 
T1-Gd +	None	≥50% decrease	<50% decrease- <25% increase	≥25% increase*	Any increase is restricted to initial RT Volume
T2/FLAIR	Stable or decrease	Stable or decrease	Stable or decrease	Increase*	Any increase is restricted to initial RT Volume
New Lesion	None	None	None	Present*	None
Corticosteroids	None	Stable or decrease	Stable or decrease	NA	Stable or decrease
Clinical Status	Stable or improved	Stable or improved	Stable or improved	Worsened*	Stable or improved
Requirement for Response	All	All	All	Any*	All

CR = complete response; PR = partial response; SD = stable disease; PD = progressive disease, PsP = Pseudoprogession

NA - Increase in corticosteroids alone will not be taken into account in determining progression in the absence of persistent clinical deterioration

1. RANO Progression occurs when any of the criteria with \* are present.
2. Confirmed PD requires all of the following If not all criteria are met then Preliminary PD
  - More than 3 months post RT
  - Radiologic progression by central review by RANO criteria
  - Clinical progression as determined by treating Oncologist
  - Cannot be considered Pseudoprogession
3. Patients with possible PsP should initially be given the Objective Status of Preliminary Progression. Once PsP or Progression is confirmed, the Objective Status can be changed accordingly. If Progressive Disease is subsequently confirmed, the Objective Status is to be recorded for the current cycle as PD (confirmed) and the back-dated date of the progressive disease (from the cycle with the initial Preliminary PD) is to be used as the date of progressive disease which is documented via the Event Monitoring Form. If progressive disease is not confirmed the Objective Status for the current cycle can be documented as SD, PR, or CR as appropriate using the baseline scan measurement as the baseline for comparison with the current measurement. The Objective Status for the cycle initially documented as Preliminary PD can be changed to PsP.

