##### 16.71 Primary Endpoint:

16.711 Definition: the primary endpoint of this trial is proportion of patients experiencing progression-free survival at 3 months. All patients meeting eligibility criteria who have a signed consent form on record and who have begun F-DOPA-guided reirradiation treatment at Mayo Clinic will be evaluable for the endpoint. All eligible patients will be followed until death or a maximum of 4 years. Time to disease progression is defined as the time from study registration to the earliest date documenting disease progression. If a patient dies without evidence of disease

progression, the patient will be censored on the last date the tumor was evaluated. If a patient is declared to be a major treatment violation, the patient will be censored on the date the treatment violation was declared to have occurred. In the case of a patient starting treatment and then never returning for any evaluation, the patient will be censored for progression on the last day of therapy.

16.712 Estimation: the proportion of successes will be estimated by the number of successes divided by the total number of evaluable patients. Confidence intervals for the true success proportion will be calculated according to the approach of Duffy and Santner.[37]

16.713 Over Accrual: if more than the target number of patients are accrued, the additional patients will not be used for evaluation of stopping rules or in any decision making process. They will be included in the final point estimates and confidence limits.

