Using the radiation treatment dosing, fractionation and normal tissue constraints outlined in Section 7 have been performed in several studies without significant adverse effects. While radiation-induced brain necrosis is rare, a cumulative normal brain dose of < 100 Gy in 2 Gy equivalents has been suggested as a constraint to minimize the risk of necrosis.[30] Two large studies reported no grade 3 or higher toxicity and no radionecrosis using the same dosing and fractionation as our protocol.[26, 27] In fact, studies using larger fraction sizes (5 Gy/fraction) reported very low rates of radionecrosis when keeping reirradiation doses under 40 Gy.[28, 29] However, tumor progression is expected in the majority of patients and commonly results in severe neurologic symptoms near the end of life. Both acute (available at <http://ctep.cancer.gov>) and late [39] toxicity will be monitored continuously as each patient is accrued and follow-up data are accumulated. If at any time, 1) 3 or more of the first 9 AE-evaluable patients; or, 2) after 10 or more patients are AE-evaluable, more than 30% experience any of the following adverse effects considered to be at least possibly related to radiation treatment up to and including the three-month timepoint; enrollment will be suspended so the details of each episode may be examined and a trial recommendation will be formulated and presented to the MCCC DSMB, adjusting the dose, fraction size or volumes as needed.

- Grade 3 or 4 irreversible CNS toxicity
- Grade 4 non-hematologic, non-CNS toxicity
- Any Grade 5 toxicity

Initial estimated Primary Completion Date: At study activation, this study will have been registered within the www.ClinicTrials.gov (CT.gov) website. The Primary and Secondary endpoints along with other required information for this study will be reported on CT.gov. For purposes of timing of the CT.gov results reporting, the initial estimated completion date of the primary endpoint of this study is 27 months after the study opens to accrual.

16.101 Definition of Primary-Endpoint Completion Date (PCD): The PCD is the date at which the last progression free patient has been followed for 3 months.

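### The primary endpoint runs on two clocks: success closes 3 months from registration, but the 3-month MRI is timed from the end of radiotherapy and normally falls after that date

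*Combined protocol and SAP*

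**What the plan says.** All references are to the combined protocol and SAP.

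- **Registration clock.** Section 16.21: "A success will be a patient who is alive and without evidence of progressive disease within 3 months from registration". Section 16.711: "Time to disease progression is defined as the time from study registration to the earliest date documenting disease progression". Both count from registration, and the second dates progression by when it is documented.
- **Post-radiotherapy wording.** Goal 2.11: "Compare the progression-free survival rate at 3 months for recurrent high-grade glioma patients after reirradiation targeting volumes designed with both" PET and MRI. Section 16.1 likewise speaks of PFS at 3 months after radiotherapy. Section 16.7 ties the start of analysis to the time points in section 4.0.
- **Scan schedule.** Section 4.0 fixes two follow-up MRIs, at 1 month (+/- 7 days) after radiotherapy and at "3 months post RT +/- 14 days". Its footnote 5 leaves the timing of other scans to the clinician.
- **Response rules.** Under section 11.416, note 2, Confirmed PD needs, among other things, more than 3 months since radiotherapy and "Clinical progression as determined by treating Oncologist"; otherwise the status is Preliminary PD. If PD is confirmed later, "the back-dated date of the progressive disease (from the cycle with the initial Preliminary PD) is to be used" as the progression date.
- **Decision rules.** Sections 16.22 and 16.23 stop the trial at 1 or fewer successes in 10 and support further testing at 6 or more in 20. Neither says whether Preliminary PD is a failure.

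**The concern.** If the success window closes before the scan that is meant to show 3-month status, a patient can already have progressed and still be counted as a success because no one has yet looked. The last required MRI inside the window is then the 1-month scan. Both decision rules use this count. With 20 patients and no control arm, one or two patients scored differently can change the result. Apart from any effect on error rates, two analysts following different sections could score the same patient differently: as a success by 16.21, and as not progression-free if 2.11 and 4.0 are taken to mean the 3-month post-radiotherapy visit.

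**Working it through.** **Plan's own figures first.** Exact two-stage binomial with the rules in 16.22 and 16.23:

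P(positive | p) = sum over x1 = 2..10 of b(10, x1, p) x P(X2 >= 6 - x1), with X2 ~ Bin(10, p).

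At p = 0.20 this gives 0.186 and at p = 0.40 it gives 0.859, both as stated in 16.21. The chance of stopping at 10 patients is 0.376 and 0.046 respectively.

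**Inputs for the dates.** Ten fractions, none at weekends or on holidays (7.53): 11 days from first to last fraction with a Monday start, 13 with any other start, longer with holidays. Three months is taken as 91 days and one month as 30. I found no limit on the gap from registration to the start of radiotherapy. It is therefore an assumption, shown for 0, 7 and 14 days.

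**Formula.** Day of the 3-month MRI from registration = gap + 11 or 13 + 91, +/- 14.

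| Gap (days) | 1-month MRI, nominal | 3-month MRI, nominal | 3-month MRI, full window |
|---|---|---|---|
| 0 | 41-43 | 102-104 | 88-118 |
| 7 | 48-50 | 109-111 | 95-125 |
| 14 | 55-57 | 116-118 | 102-132 |

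The 3-month MRI reaches day 91 only if gap + 11 + 77 <= 91, a gap of at most 3 days with a Monday start, or gap + 13 + 77 <= 91, a gap of at most 1 day otherwise. In either case the scan must be at or near the early edge of its window. Section 13.1 allows for a registered patient who has not yet had the planning PET, so so short a gap is unlikely to be usual.

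**Consequence.** Take a patient whose tumour progresses after the 1-month MRI and before day 91 without clinical signs, with no discretionary scan in between. The first documentation is the 3-month MRI, after day 91. By 16.21 and 16.711 this patient is a success. Back-dating under 11.416 does not change that, because the first Preliminary PD is that same scan.

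**What moving to the scan date would do to the design.** If 20% and 40% are day-91 rates and PFS is exponential (an assumption), then p(d) = p^(d/91). With the 6/20 rule unchanged:

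| Day | p0 | p1 | Alpha | Power | P(stop at 10) at p1 |
|---|---|---|---|---|---|
| 102 | 0.165 | 0.358 | 0.092 | 0.759 | 0.078 |
| 104 | 0.159 | 0.351 | 0.080 | 0.738 | 0.085 |
| 109 | 0.145 | 0.334 | 0.056 | 0.684 | 0.104 |
| 118 | 0.124 | 0.305 | 0.028 | 0.582 | 0.142 |

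**The case against.** The strongest reply has four parts.

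1. **The post-radiotherapy reading has support.** Section 16.7 points the analysis to section 4.0, whose only 3-month point is after radiotherapy, and 2.11 and 16.1 use similar wording. This stands as far as it goes. It does not override the explicit definitions in 16.21 and 16.711, but it means that the scoring consequence follows on one of two readings.

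2. **The response rules govern much silent change on either clock.** Confirmed PD requires clinical progression, so a silent increase is at most Preliminary PD when first seen. Under 11.415, an increase confined to the initial radiation volume in a stable patient meets the pseudoprogression criteria, and section 1.6 puts 60-70% of recurrences after reirradiation in-field. This also stands. The clock decides the score clearly only for new or out-of-field lesions, and for Preliminary PD that is later confirmed and back-dated to the 3-month scan.

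3. **Some cases are caught, and some are not errors.** Clinical deterioration, death or a discretionary scan before day 91 will identify some failures in time. Progression that truly begins after day 91 is properly a success on the registration clock.

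4. **The null is not clearly a day-91 figure.** Under exponential PFS, 20% at time t implies a median of t x ln 2 / ln 5: 1.29 months at day 91, and 1.45-1.67 months at days 102-118 (30.4 days per month). All lie within the 1-2 months cited in 16.21.

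A reader might also infer from the completion-date text ("the initial estimated completion date of the primary endpoint of this study is 27 months after the study opens to accrual") that the sponsor meant the registration clock, since 24 months of accrual (16.4) plus 3 is 27. That is too weak to use. The date is an estimate in whole months, the post-radiotherapy clock would give 27.4-27.9, and 22 patients at 10 per year already need 22/10 x 12 = 26.4 months. The definition in 16.101 ("The PCD is the date at which the last progression free patient has been followed for 3 months") names no starting point for the 3 months.

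**Conclusion.** The inconsistency is real: the operative definition and the scan schedule use different starting points, and no passage says which scan decides the endpoint. On the registration clock the effect has one direction. Compared with an assessment at day 91, it can only add successes at the 10- and 20-patient rules.

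A reader might go further and conclude that the true type I error exceeds 0.186 by a particular amount, or that the trial is biased in favour of the treatment. The documents do not support that. They give neither the share of patients with silent progression in this interval nor the gap from registration to radiotherapy, and the published PFS behind the 20% null may carry a scan-timing effect of its own.

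The date ranges rest on 91 days for 3 months, no holidays and an assumed gap of 0-14 days. The point should be fixed before the endpoint is scored.

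**What to change.** **Clock and deciding scan.** Reconcile 2.11, 4.0, 16.1, 16.21, 16.7, 16.711 and the completion-date text with 16.101. Define success as alive with no progression on any assessment from registration up to and including the scheduled 3-month post-radiotherapy MRI (+/- 14 days). State how a patient who is alive but lacks that MRI is scored.

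**Rates.** State that 20% and 40% refer to that timepoint, in which case alpha 0.186 and power 0.859 stand. Otherwise restate the rates and the decision rule.

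**Preliminary PD, as a separate item.** State how Preliminary PD at that scan counts for the 10- and 20-patient rules, consistent with 11.414-11.416 and with a fixed data cut-off. The choice of rule is the sponsor's.

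**Cost.** Wording only, with no added scan. Three consequences should be accepted openly:

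- The endpoint becomes stricter by about 11-27 days (102 - 91 to 118 - 91), and time at risk varies with the scan date, from about day 88 to day 132 for gaps of 0-14 days.
- The completion date moves by about 0.4-0.9 month at the nominal scan (24 + 102/30.4 = 27.4; 24 + 118/30.4 = 27.9), before any data cut-off.
- If 20% and 40% are really day-91 rates, keeping 6/20 under the exponential assumption gives alpha 0.08-0.09 and power 0.74-0.76 at day 102-104, and alpha 0.03-0.06 and power 0.58-0.68 at day 109-118. This is why the rates must be tied to a timepoint in the same amendment.

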### 16.3 Sample Size

The design to be utilized is fully described in section 0. A maximum of 20 evaluable patients will be accrued to this pilot study unless undue toxicity is

encountered. We anticipate accruing an additional 2 patients to account for ineligibility, cancellation, major treatment violation or other reasons. Maximum projected accrual is therefore 22 patients. We anticipate screening 30 patients to register a total of 22 patients necessary for study design.

#### 16.4 Accrual Time and Study Duration

Based on institutional experience, we deliver RT to an average of 25 recurrent glioma patients annually. Our plan to accrue 10 patients per year is based on including less than 50% of our recurrent glioma RT population, which is readily achievable. We plan to accrue patients for years 1-2, leaving years 3-4 for follow-up and analysis. Therefore, the overall study duration is expected to be 48 months.

#### 16.5 Power and Significance Levels

Assuming the number of successes is binomially distributed, the significance level is 0.186 and probability of declaring that this regimen warrants further studies (i.e. statistical power) under various success proportions and the probability of stopping accrual after the first stage can be tabulated as a function of the true success proportion as shown in the following table.

#### 16.6 Other considerations:

Adverse events and patterns or failure observed in this study as well as scientific discoveries or changes in standard care will be taken into account in any decision to terminate the study.

#### 16.7 Analysis plan

The analysis for this trial will commence at the planned time points (see Section 4.0) and at the time patients have become evaluable for the primary endpoint. Such decisions will be made by the statistician and the study chair, in accord with the Cancer Center Statistics (CCS) Standard Operating Procedures, availability of data for secondary endpoints, and level of data maturity. The earliest date anticipated in which results will be available for manuscript, abstract or presentation format is when 20 patients have either progressed or been followed for at least 3 months. Subgroup analyses will be included for this primary endpoint to assess known prognostic factors such as MGMT status, age, and time from prior RT to reirradiation.

##### 16.71 Primary Endpoint:

16.711 Definition: the primary endpoint of this trial is proportion of patients experiencing progression-free survival at 3 months. All patients meeting eligibility criteria who have a signed consent form on record and who have begun F-DOPA-guided reirradiation treatment at Mayo Clinic will be evaluable for the endpoint. All eligible patients will be followed until death or a maximum of 4 years. Time to disease progression is defined as the time from study registration to the earliest date documenting disease progression. If a patient dies without evidence of disease

progression, the patient will be censored on the last date the tumor was evaluated. If a patient is declared to be a major treatment violation, the patient will be censored on the date the treatment violation was declared to have occurred. In the case of a patient starting treatment and then never returning for any evaluation, the patient will be censored for progression on the last day of therapy.

16.712 Estimation: the proportion of successes will be estimated by the number of successes divided by the total number of evaluable patients. Confidence intervals for the true success proportion will be calculated according to the approach of Duffy and Santner.[37]

16.713 Over Accrual: if more than the target number of patients are accrued, the additional patients will not be used for evaluation of stopping rules or in any decision making process. They will be included in the final point estimates and confidence limits.

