### 7.2 F-DOPA-PET

#### 7.21 Timing of PET scanning:

The PET scan to be used for radiation treatment planning should be acquired no more than 14 days prior to beginning radiation treatments.

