### 13.0 Treatment/Follow-up Decision at Evaluation of Patient

- 13.1 A patient is deemed *ineligible* if after registration, it is determined that at the time of registration, the patient did not satisfy each and every eligibility criteria for study entry. The patient will go off study.
- If the patient received MR and PET for radiotherapy planning, all data up until the point of confirmation of ineligibility must be submitted.
  - If the patient never received pre-RT PET, on-study material must be submitted. No additional follow up is necessary.
- 13.2 Those patients who will not receive any radiation treatment or who will receive radiation treatment elsewhere (not at Mayo Clinic) will be considered non-evaluable for the study endpoint and move to Event Monitoring phase per Section 18.0.
- 13.3 Patients who are CR, PR, REGR, or SD will continue to obtain MRI scans at each clinically indicated follow-up for up to 2 years from registration.
- 13.4 Patients who develop PD or withdraw from further follow-up scans will go to the event-monitoring phase per Section 18.0.

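### The 3-month clock starts at registration, but only patients who begin reirradiation are counted, so registered patients who die or deteriorate and never start it drop out of the success proportion

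*Combined protocol and SAP*

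**What the plan says.** **Clock.** Section 16.21 defines the outcome from registration: "A success will be a patient who is alive and without evidence of progressive disease within 3 months from registration". Section 16.711 uses the same origin: "Time to disease progression is defined as the time from study registration to the earliest date documenting disease progression".

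**Denominator.** Section 16.711 requires that the patient is eligible, has consented and has begun the PET-guided treatment; such patients on "reirradiation treatment at Mayo Clinic will be evaluable for the endpoint". Section 16.712 then states that "the proportion of successes will be estimated by the number of successes divided by the total number of evaluable patients".

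**Non-starters.** Under section 13.2, patients who get no radiation, or get it elsewhere, "will be considered non-evaluable for the study endpoint and move to Event Monitoring phase". Death and progression are not treated differently from other reasons. Section 16.3 allows 2 registrations beyond the 20 evaluable patients for ineligibility, cancellation, major violation and other reasons.

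**Gap.** The test schedule in section 4.0 lists the PET scan under treatment planning, separately from the pre-registration baseline. Section 7.21 ties the scan to radiotherapy: "The PET scan to be used for radiation treatment planning should be acquired no more than 14 days prior to beginning radiation treatments". I found no maximum interval from registration to radiotherapy, and no planned analysis from the first fraction or in all registered patients.

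**The concern.** A treated-patient set is a reasonable target, and so is a registration origin. Combined, they do not match. Entry to the set depends on something that happens after the clock has started. Anyone who dies or deteriorates too far to be treated in that interval leaves the calculation and is replaced, and everyone who remains has by construction lived to the first fraction.

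The interval matters in this population. Eligibility extends to ECOG 3, and section 16.21 cites a median PFS of 1 to 2 months after bevacizumab failure as the basis for the null. With 20 evaluable patients and a threshold of 6 successes, replacing one early failure could change the decision.

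**Working it through.** **Inputs from the plan.** Stop if 1 or fewer of the first 10 evaluable patients succeed (16.22). The result is positive if 6 or more of 20 succeed (16.23). Null 20%, alternative 40%, alpha 0.186, power 85.9% (16.21). Two extra registrations (16.3).

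**Assumed, because the documents do not give it.** The number of registered patients who fail and therefore never start radiotherapy: 1 in 21, or 2 in 22.

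**Step 1: reproduce the design.** With success probability p,

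P(positive) = Σ over x = 2 to 10 of P(X₁ = x) × P(X₂ ≥ 6 − x), where X₁ and X₂ are each binomial(10, p).

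At p = 0.20:

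| x in first 10 | P(X₁ = x) | P(X₂ ≥ 6 − x) | Product |
|---|---|---|---|
| 2 | 0.3020 | 0.1209 | 0.0365 |
| 3 | 0.2013 | 0.3222 | 0.0649 |
| 4 | 0.0881 | 0.6242 | 0.0550 |
| 5 | 0.0264 | 0.8926 | 0.0236 |
| 6 or more | 0.0064 | 1 | 0.0064 |

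The sum, before rounding of the terms, is 0.1863. At p = 0.40 the same formula gives 0.8586. Both match the plan. A single-stage rule of 6 in 20 would give 0.1958 and 0.8744, so the stated figures belong to the two-stage rule.

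**Step 2: condition on starting radiotherapy.** Let a share f of registered patients fail before radiotherapy and never start it. They are all failures, so removing them leaves the number of successes unchanged and shrinks the denominator: p(evaluable) = p(registered) / (1 − f). With 20% true success among all registered patients:

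| Failures never starting / registered | p(evaluable) | P(positive) |
|---|---|---|
| 0 of 20 | 20.0% | 0.186 |
| 1 of 21 | 0.20 / (20/21) = 21.0% | 0.219 |
| 2 of 22 | 0.20 / (20/22) = 22.0% | 0.254 |

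**Step 3: the decision boundary.** Six successes are 6/20 = 30.0% of evaluable patients. Against 22 registered they are 6/22 = 27.3%.

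**Step 4: the other reading.** Suppose the target is treated patients. A patient who is event-free at the first fraction, a gap g after registration, then has to stay event-free for only 3 months minus g. That is easier than staying event-free for 3 months after treatment starts. The direction is again upward, without any dropout. Its size depends on g, which the plan does not state.

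**The case against.** Several counter-arguments carry weight.

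- **The alpha claim is conditional.** A reader might infer that the false-positive rate simply exceeds 0.186. The documents do not support that. Section 16.21 describes the proportion among patients treated with PET-guided radiotherapy, and for a 20% rate in that set as measured, alpha is 0.186. Inflation follows only if the 20% refers to all registered patients, or to a clock that starts at radiotherapy. The time origin of the series behind the 20% is not given.
- **Not every early failure leaves.** A reader might infer that anyone who progresses before radiotherapy is excluded. Section 13.2 removes only those who never receive radiation on study. A patient who progresses and still starts stays in the denominator as a failure. The planning scan is the only MRI scheduled between registration and treatment, so losses would come mainly from death or from deterioration that cancels treatment.
- **Some losses are unrelated to outcome.** A positive pregnancy test, tracer allergy, ineligibility and treatment elsewhere need not bias the proportion, and the 2-patient allowance has to absorb these as well.
- **A larger size is tempting.** Take a constant hazard that leaves 20% event-free at 3 months, assume gaps of 7, 14 or 21 days, and drop every early event. The false-positive rate becomes 0.28, 0.39 or 0.53. As a denominator effect this does not fit the plan. Losses of 11.6%, 21.9% and 31.0% would need 20/0.884 = 22.6, 20/0.781 = 25.6 and 20/0.690 = 29.0 registrations, against a stated maximum of 22. The gaps are assumed, and patients who progress but still start would be wrongly removed.
- **Deaths alone may do little.** Section 1.6 gives a median survival of 7 to 10 months after reirradiation. With exponential deaths and an assumed gap of 7 to 14 days, 1.6% to 4.5% would be lost. The evaluable rate would be 20.3% to 20.9% and the false-positive rate 0.197 to 0.217. Deterioration short of death adds an unknown amount.

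A positive result also leads only to a possible recommendation for further testing. These points limit the size. They do not remove the mismatch, because a treated-patient target calls for a clock that starts with treatment.

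**Conclusion.** The mismatch is in the current text. The 3 months run from registration, while the denominator holds only patients who began reirradiation. Registered patients who die or deteriorate and therefore never start are dropped and replaced, and treated patients are credited with the time before radiotherapy. The bias is upward.

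Its size cannot be fixed from the documents. If the 20% null is a rate among all registered patients, one such loss in 21 moves the false-positive rate from 0.186 to 0.219. Two in 22 moves it to 0.254, which is a ceiling under the planned accrual, since it spends the whole allowance on outcome-related losses. These figures rest on the plan's two-stage rule and on the assumed number of losses. If the null was meant for the treated set exactly as defined, alpha stays at 0.186, but the plan does not say so. The point deserves correction before analysis but does not invalidate the design.

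**What to change.** 1. In sections 16.21 and 16.711, keep the treated set and start the 3 months at the first reirradiation fraction. This fits goal 2.11, which speaks of progression-free survival after reirradiation. State that the 20% null refers to the same set and origin.
2. Report the number of eligible registered patients who never start, with reasons.
3. Add a sensitivity analysis from registration that includes all eligible registered patients and counts those who die or progress before radiotherapy, and so never start it, as failures.
4. State a rule for non-starters whose 3-month status is unknown. It is needed because section 18.1 collects Event Monitoring data yearly, at progression and at death, with no 3-month assessment. One option is to count them as failures and show the opposite assumption beside it.

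The cost is a few sentences and one more analysis. A radiotherapy reporting form, an off-treatment form for withdrawal before radiotherapy, and progression and survival follow-up are already planned. The downside for the sponsor is a possibly slightly lower success proportion. Counting eligible non-starters who fail as failures, in a set of 20, would restore alpha 0.186 and power 85.9% for the registered population.
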